6. SAFETY REVIEW COMMITTEE AND DATA MONITORING COMMITTEE

6.1. Safety Review Committee

To monitor patient safety, data will be reviewed regularly by the Investigator or designee throughout the study. [REDACTED]

[REDACTED] The SRC will review [REDACTED] data for each individual at the following time points:

- [REDACTED] in advance of the first dose adjustment [REDACTED]
- At any other time during the study, as requested by the Investigator or Sponsor, [REDACTED]

Note that the DMC also will review each patient's record [REDACTED], prior to any study dose escalation [REDACTED]. Further information on the DMC is available in [Section 6.2](#).

[REDACTED] Based on SRC review of the available data, [REDACTED]

the SRC may recommend stopping, increasing, decreasing, or maintaining (current dose) the dose of ORGN001.

The Investigator or Sponsor may also convene the SRC for unscheduled dose adjustments, based on drug-related AEs or changes in clinical parameters.

6.1.1. Safety Criteria for Unscheduled Dose Adjustments

Doses may be adjusted, based on drug-related AEs or changes in clinical parameters and laboratory data. Dose changes will occur following consultation with the medical monitor and, if applicable, with the SRC. If a patient has significant clinical worsening related to ORGN001 dosing, the dose may be decreased, based on the patient's clinical status and, if available, exposure data.

6.1.2. Criteria for Adjustment or Stopping Doses

The following are examples of possible clinical conditions and potential actions to be taken with respect to study drug administration in a given child or group of children. This list is not comprehensive. Consideration of dose changes for each patient will be assessed individually by the treating physician, based on the patient's clinical status and review with the medical monitor.

- Scenario 1: Any study drug-related SAE that results in the death of a single patient

Action: No further dose escalations will take place in any patient; pending evaluation, all other patients will maintain their current dose level and no new patient will be enrolled in the study. A substantial amendment to the Clinical Trial Authorization will be submitted

to the relevant Competent Authorities for approval prior to restarting enrollment and allowing further dose escalations in the event that any study drug-related SAE results in the death of a single patient.

- Scenario 2: One or more study drug-related SAEs in a single patient

Action: If the treating physician, in consultation with the medical monitor, determines that a dose reduction could be expected to reduce the risk of the SAE and not increase the risk of MoCD-related symptoms, the patient may be treated with a lower dose of ORGN001. Subsequent dose escalation for that patient may be considered, based on clinical assessment by the treating physician in consultation with the medical monitor.

- Scenario 3: The same study drug-related SAE occurs in 2 different patients.

Action: In addition to the actions taken under Scenario 2, dosing in subsequent patients may be limited, to achieve concentrations below those observed in the patients with drug-related SAEs, patient to clinical assessment by the treating physician in consultation with the medical monitor.

- Scenario 4: PK exposure in a single patient exceeds the AUC NOAEL limit by greater than 10%

Action: The patient's dose is reduced to a dose level that results in exposure that is below the NOAEL exposure.

6.1.3. Criteria for Site or Study Termination

For reasonable cause, the Investigator, Institutional Review Board (IRB)/Ethics Committee (EC), or Sponsor may terminate the study at a given center, in which case, patient care would be transferred to a different Investigator. If all centers are terminated, patients would return to the care of their treating physicians. Conditions that may warrant termination of the study or investigational sites include, but are not limited to:

- Discovery of an unexpected, serious, or unacceptable risk to patients enrolled in the study
- Sponsor decision to suspend or discontinue testing, evaluation, or development of the ORGN001
- Failure of the Investigator to comply with the approved protocol, pertinent guidelines, and/or regulations
- Submission of false information knowingly from the Investigator to the Sponsor and/or regulatory authorities

6.2. Data Monitoring Committee

[figure not shown]
[REDACTED] The DMC will have access to all safety data, in accordance with its primary function of ensuring patient safety. The DMC may make

recommendations to the Sponsor regarding safety issues, study conduct, and/or modifying, extending, or stopping the study.

The DMC will review each patient's record [REDACTED], prior to any study dose escalation [REDACTED]

[REDACTED]. The SRC may request additional ad hoc DMC meetings, as needed.

Each member of the DMC will be required to sign a contract agreement, including confidentiality and financial disclosure statements, assuring no conflicts of interest, as a condition for membership on the committee.

6.3. Definition of Study End

The end of the study will be defined as the date of the last patient's last visit.

After Month 36, treatment with ORGN001 may be continued if determined to be clinically indicated. Due to the rare nature of the disease and no currently available treatment, patients exceeding 36 months of treatment may continue to receive study drug until ORGN001 becomes commercially available or development has stopped.

7. SELECTION AND WITHDRAWAL OF PATIENTS

7.1. Patient Recruitment and Consent

Eligible patients will be identified via prenatal diagnosis of MoCD Type A, or as soon as possible after birth, based on genetic evaluation or, if no prenatal diagnosis is made, presentation of signs and symptoms consistent with MoCD Type A. The Investigator at each site will be responsible for discussing therapeutic options for the patient with his/her parent or legal guardian.

Should a parent or legal guardian choose to enroll his/her child in this study, he/she will have to provide informed consent. Before recruitment and enrollment, the parent or legal guardian of each prospective patient will be given a full explanation of the study by the Investigator or his/her designee and will be allowed to read the approved Informed Consent Form (ICF). After a comprehensive description of the protocol, review of the ICF, and all questions have been answered, the patient's parent or legal guardian will have the opportunity to decide if he/she wants the child to participate in the study. Once the Investigator is assured that the patient's parent or legal guardian understands the implications of participating in the study, written informed consent must be obtained. The site will keep the original ICF and provide a copy to the parent/legal guardian. After the ICF is signed, the patient will be assessed for eligibility for inclusion into the study. Informed consent must be obtained prior to performing any study-related procedures and may be obtained before the Screening/Baseline Visit.

Legal guardians who have their child diagnosed with MoCD Type A prenatally may be asked to sign a separate ICF to allow study procedures to begin on their child as soon after birth as possible.

7.2. Patient Inclusion Criteria

Patients must meet all of the inclusion criteria to be considered eligible for enrollment in this study.

- Male or female neonatal patients (1 to 28 days of age [inclusive] at the time of ORGN001 administration, with day 1 of age corresponding to the day of birth), or infant (29 days to < 2 years of age) or child (2 to 5 years of age [inclusive]) with MoCD Type A, previously untreated with ORGN001 or treated with ORGN001 through the EAP
- In neonates, diagnosis of MoCD Type A, based on:
 - Prenatal genetic diagnosis, or
 - Onset of clinical and/or laboratory signs and symptoms consistent with MoCD Type A (eg, seizures, exaggerated startle response, high-pitched cry, axial hypotonia, limb hypertonia, feeding difficulties, elevated urinary sulfite and/or SSC, elevated xanthine in urine or blood, or low or absent uric acid in the urine or blood) within the first 28 days after birth
- In infants or children, diagnosis of MoCD Type A, based on:

- Confirmed genetic diagnosis (genetic confirmation of the diagnosis of MoCD Type A may be obtained after initiation of ORGN001 therapy in certain cases), biochemical profile, and clinical presentation consistent with MoCD Type A
- Parent or legal guardian must have signed the ICF prior to any study procedures being performed

7.3. Patient Exclusion Criteria

Patients will be excluded from participating in the study if they meet any of the following criteria:

- Diagnosis other than MoCD Type A (may be determined after the initiation of study drug)
- Condition that is considered by the treating physician to be a contraindication to therapy, including evidence of abnormalities on brain imaging not attributable to MoCD, or that might otherwise interfere with the patient's participation in the study, pose any additional risk for the patient, or confound patient assessments
- Antenatal and/or postnatal brain imaging prior to initiation of treatment with ORGN001 that indicates cortical or subcortical cystic encephalomalacia, clinically significant intracranial hemorrhage, or other abnormalities on brain imaging determined by the treating physician to be clinically significant
- mGCS for Infants and Children score of less than 7 for more than 24 hours (does not apply to children less than 1 day in age)

7.4. Patient Withdrawal Criteria

The study staff should notify the Sponsor and the site monitor of all study withdrawals as soon as possible. The patient's parent/legal guardians may withdraw consent at any time. Every effort should be made to ensure that the patient's parents/legal guardians are willing to comply with study participation, prior to conducting the Screening/Baseline procedures.

Investigators may choose to discontinue a patient's treatment due to an AE, as well as conditions or illnesses that preclude compliance with the protocol from the standpoint of the patient's safety or wellbeing (safety, behavioral, or administrative reasons). Patients may be withdrawn from the study for reasons including, but not limited to:

- Diagnosis other than MoCD Type A
- The discretion of the Investigator, in consultation with the medical monitor/SRC, as appropriate, regarding an AE or other medical reason (eg, clinically significant Baseline abnormalities on MRI or brain ultrasound)
- Patient (and/or parent or legal guardian) request
- Patient and/or parent or legal guardian is unwilling or unable to adhere to the protocol requirements

All patients who discontinue or are withdrawn from the study will be encouraged to complete the Safety Follow-up Visits [REDACTED] following treatment discontinuation,

whenever possible. The reasons for premature study withdrawal must be recorded in the patient's CRF and in the source records.

For patients who are prematurely withdrawn from the study due to clinical findings (eg, AE[s]), the Investigator must immediately notify the Sponsor's medical monitor. In these patients, AEs leading to premature withdrawal must be followed until resolution of the event or the patient is determined to be medically stable, in the opinion of the Investigator. Patients who withdraw from the study will not be replaced.

Patients who withdraw from the study will return to the care of their treating physician.

8. TREATMENT OF PATIENTS

This is an open-label study designed to evaluate the safety and efficacy of ORGN001 administered to neonates, infants, and children with MoCD Type A. All enrolled neonate patients meeting inclusion and exclusion criteria will receive treatment with study drug (ORGN001 infusion) as soon as possible after birth.

8.1. Description of Study Drug

Table 13: ORGN001 Description

	Study Drug
Product Name	ORGN001
Dosage Form	Powder for solution for infusion
Potency	[REDACTED]
Route of Administration	IV use
Physical Description	Sterile, [REDACTED] white to slightly yellow lyophilized powder
Manufacturer	[REDACTED]

8.2. Prior and Concomitant Medications and Procedures

Prior medications, defined as any drug or substance taken by the patient within 28 days prior to the time the parent or legal guardian signs the ICF until the first ORGN001 dose, and concomitant medications, defined as any drug or substance taken by the patient after the first ORGN001 dose until completion of the last study visit, will be recorded on the patient's CRF.

Prior procedures, defined as any therapeutic intervention (eg, surgery/biopsy, physical therapy) performed within 28 days prior to the time the parent or legal guardian signs the ICF until the first ORGN001 dose (not to exclude the collection of data on relevant procedures as part of Medical History conducted more than 28 days prior to consent), and concomitant procedures, defined as any therapeutic intervention (eg, surgery/biopsy and physical therapy) performed after the first ORGN001 dose drug until completion of the last study visit, will be recorded on the patient's CRF. If possible, elective surgical procedures should not be performed during the initial 12-month study period.

[figure not shown]
ORGN001 is not an inhibitor of cytochrome P450 (CYP450) enzymes *in vitro*; therefore, concurrent administration of ORGN001 is unlikely to affect systemic exposure of other CYP substrates. CYP isoforms responsible for biotransformation of ORGN001 are unknown.

Changes in a patient's anticonvulsants, including the reason for the change, will be recorded. Adverse events related to administration of these therapies or procedures must be documented on the appropriate CRF.

8.3. Treatment Adherence

The Investigator or designee must ensure that the parent or legal guardian of each study patient is adequately informed of the study drug regimen required for compliance with the study protocol. Daily infusions of ORGN001 at home will be administered by the patient's parent or legal guardian with the support, [REDACTED]. If a parent or legal guardian is unable to administer ORGN001 on a given day, study drug may be administered by an alternate caregiver, provided that training for ORGN001 administration by

the alternate caregiver has been documented. Patient adherence to the study drug regimen will be monitored throughout the study by reviewing study drug administration records and study drug accountability. Study drug accountability (including accounting of study drug returns) will be reviewed with the patient's parent or legal guardian at each study visit.

Missed treatments must be clearly documented in the patient's study records and recorded in the CRF. Additionally, these must be documented as protocol deviations.

9. STUDY DRUG MATERIALS AND MANAGEMENT

9.1. Study Drug

ORGN001 drug product [REDACTED] is a sterile, nonpyrogenic, white to slightly yellow lyophilized powder in a stoppered, [REDACTED] vial. The drug product is designed to be reconstituted in [REDACTED] sterile Water for Injection and administered by IV infusion. [REDACTED]
[REDACTED]
[REDACTED]
[REDACTED]

[REDACTED]

[REDACTED]

[REDACTED]

[REDACTED]

[REDACTED]

[REDACTED]

[REDACTED]

[REDACTED]

[REDACTED]

9.3. Study Drug Storage

ORGN001 vials must be stored frozen at -10°C to -25°C and protected from light. Following reconstitution, ORGN001 should be administered within 4 hours. Reconstituted ORGN001 may be stored at 2°C to 8°C or room temperature prior to administration. If stored at 2°C to 8°C, reconstituted ORGN001 should be allowed to come to room temperature before infusion. Reconstituted ORGN001 must not be heated [REDACTED]
other than by ambient air temperature. [REDACTED]

9.4. Study Drug Preparation

To account for the impact of body weight on the mass (mg) of administered study drug, body weight will be assessed [REDACTED]

[REDACTED] The dose may be adjusted due to weight changes recorded by the home caregiver and/or physician visits with proper documentation.

Reconstitute ORGN001 with [REDACTED] sterile Water for Injection.

[REDACTED]

[REDACTED]

9.5. Study Drug Administration

Starting on Day 1, patients will begin daily IV infusions of ORGN001 at a dose of either 700 $\mu\text{g}/\text{kg}$ (term neonates, infants, and children) or 525 $\mu\text{g}/\text{kg}$ (preterm neonates). ORGN001 drug product is to be administered at an infusion rate of 1.5 mL/min, [REDACTED] [REDACTED]. Based on a review of Day 1-related exposure parameters, each patient's dose may be initially escalated [REDACTED] with incremental increases up to 1200 $\mu\text{g}/\text{kg}/\text{day}$ by Month 3.

[REDACTED]

[REDACTED]

[REDACTED] The parent, legal guardian, and any authorized caregiver will be trained on proper storage, preparation, and administration of study drug for dosing at home, [REDACTED]

[REDACTED].

[REDACTED]

9.6. Study Drug Accountability

Each investigational study site must maintain accurate records demonstrating dates and amount of study drug received, to whom dispensed (patient-by-patient accounting), and accounts of any study drug accidentally or deliberately destroyed.

Unless otherwise notified, all vials, both used and unused, must be saved for study drug accountability. At the end of the study, a final reconciliation must be made between the amount of study drug supplied, dispensed, and subsequently destroyed or returned to the Sponsor.

A written explanation will be provided for any discrepancies. After reconciliation, the Investigator must destroy or return all unused vials of study drug, as instructed by the Sponsor.

If any study drug supplies are to be destroyed at the site, the Investigator must obtain prior approval by the Sponsor. The Investigator must notify the Sponsor, in writing, of the method, the date, and the location of destruction.

Destruction of unused vials of study drug by the Investigator must be in compliance with federal, state, country, and local regulations.

9.7. Study Drug Handling and Disposal

ORGN001 should be handled with care. Aseptic technique should be used for dose preparation. In the event of a spill, use universal precautions for clean-up. Dispose of any spilled material in

compliance with federal, state, country, and/or local regulations. [REDACTED]
[REDACTED]

10. PHARMACODYNAMICS ASSESSMENTS

Pharmacodynamic assessments will be performed using spot urine samples collected at all study visits, [REDACTED] and using venous blood samples collected predose [REDACTED]
[REDACTED].

Pharmacodynamic assessments also will be collected at Safety Follow-up Visits and any unscheduled dose adjustment visits.

An alternative blood sampling schedule for infants, for whom less blood volume should be collected, must be used [REDACTED]
[REDACTED].

Samples will be evaluated for biomarkers of the MoCD pathway including, but not limited to: SSC,
[REDACTED]
[REDACTED]
[REDACTED]

Prior to first infusion, at least 1 blood sample and 1 urine sample must be collected.

Following recommendation by the SRC for an unscheduled dose adjustment, additional blood and urine samples will be collected to evaluate changes in SSC, xanthine, uric acid, urinary creatinine, [REDACTED] as follows:

- On the first day the adjusted dose is administered, the patient will be administered study drug in-clinic, and a pre-dose blood sample will be collected on the [REDACTED] day of the dose adjustment [REDACTED]. A urine sample will be collected at any time during [REDACTED] the dose adjustment visit.
[REDACTED]
[REDACTED]
- At any Safety Follow-up Visit, a PD blood sample [REDACTED] will be collected.

Under no circumstance will the total blood volume obtained exceed the amount considered acceptable for the patient's clinical condition and the institution's guidelines [REDACTED]
[REDACTED]. If an Investigator decides to deviate from these limits, the deviation must be fully documented, and the Investigator should provide justification for the deviation.
[REDACTED]
[REDACTED]
[REDACTED]

11. PHARMACOKINETICS ASSESSMENTS

Pharmacokinetic assessments will be performed [REDACTED] [REDACTED]. Pharmacokinetic samples also will be collected at Safety Follow-up Visits and any unscheduled dose adjustment visits.

An alternative blood sampling schedule for infants, for whom less blood volume should be collected, must be used [REDACTED] [REDACTED].

Blood samples will be collected for assessment of PK parameters (C_{max} , AUC, $t_{1/2}$). Details of PK sampling time points are specified below. Dosing date, time, amount, precise time of infusion prior to PK sample collection, and exact time of PK sample collection must be recorded in the CRF.

Pharmacokinetic samples will be collected [REDACTED]

: [REDACTED]

- Pre-dose at Day 1 only
- at the EOI ± 5 minutes
- 1 to 2 hours after EOI
- 3 to 4 hours after EOI

If the PK collection kit is not available for Day 1 PK sample collection, samples may be drawn any time from Day 2 to Day 7, when the patient is still in the hospital. In such a case, PK samples should be collected using the following schedule:

- at the EOI ± 5 minutes
- 1 to 2 hours after EOI
- 3 to 4 hours after EOI

Day 1 PK samples will be analyzed and PK assessment completed in time for a scheduled combined SRC/DMC meeting prior to each patient's recommended [REDACTED] dose escalation [REDACTED]

[REDACTED]

[REDACTED]

[REDACTED]

Following recommendation by the SRC for an unscheduled dose adjustment, blood samples will be collected for assessment of PK parameters, as follows:

- On the [REDACTED] day the adjusted dose is administered, the patient will be administered study drug in-clinic, and a blood sample will be collected at the EOI (± 5 minutes), 1 to 2 hours after the EOI, and at 3 to 4 hours after the EOI. The time of infusion, PK

sample collection, the dose administered, and the start and stop time of IV infusion are to be recorded in the CRF. [REDACTED] following an unscheduled dose adjustment, a PK sample will be collected at 1 to 2 hours after EOI.

[REDACTED]

Under no circumstance will the total blood volume obtained exceed the amount considered acceptable for the patient's clinical condition and the institution's guidelines [REDACTED]. If an Investigator decides to deviate from these limits, the deviation must be fully documented, and the Investigator should provide justification for the deviation.

[REDACTED]

[REDACTED]

[REDACTED]

12. EFFICACY ASSESSMENTS

Efficacy assessments are described in [Sections 4.3.9, 4.3.10, 4.3.11, 4.3.12, 4.3.13, 4.3.14, 4.3.15, 4.3.16, 4.3.17, 4.3.19, 4.3.20](#), and [4.3.21](#).

13. SAFETY ASSESSMENTS

Safety assessment data are collected from the time of signing informed consent, [REDACTED]

[REDACTED]

13.1. Physical and Neurological Examination

A complete physical examination, [REDACTED]

[REDACTED] will be performed

[REDACTED].

13.2. Vital Signs

[REDACTED] At all outpatient study visits, the vital sign measurement to be recorded in the CRF is the first set of vital signs taken.

13.3. Laboratory Assessments

[REDACTED] The Investigator or delegate will review, sign, and date laboratory reports, as well as indicate if abnormal results are clinically significant or not clinically significant. Abnormal results will be followed, at the discretion of the Investigator. An alternative blood sampling schedule for infants, for whom less blood volume should be collected, must be used [REDACTED]

Following recommendation by the SRC for an unscheduled dose adjustment, blood and urine samples will be collected for assessment of hematology, serum chemistry, and urinalysis as follows:

- On the day of dose change, study drug will be administered at the study site. A urine sample will be collected.
- Seven days after the adjusted dose is administered, a blood and a urine sample will be collected at any time during this study visit.

Under no circumstance will the total blood volume obtained exceed the amount considered acceptable for the patient's clinical condition and the institution's guidelines [REDACTED]. If an Investigator decides to deviate from these limits, the deviation must be fully documented, and the Investigator should provide justification for the deviation. [REDACTED]

[REDACTED]

Hematology samples will be analyzed for CBC, which includes platelet count, red blood cell (RBC) count, white blood cell count and automated differential (neutrophils, lymphocytes, monocytes, eosinophils, basophils), hemoglobin, hematocrit, and RBC indices (mean corpuscular volume, mean corpuscular hemoglobin, and mean corpuscular hemoglobin concentration).

Serum chemistry samples will be analyzed for electrolytes, BUN, creatinine, calcium, ALT, AST, alkaline phosphatase, total bilirubin, total serum albumin, and serum osmolality.

Urine samples will be analyzed for specific gravity, pH, glucose, protein, blood and ketones (by dipstick and microscopic examination), and urine protein to creatinine ratio.

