This study will include a Screening Period, a 12-month Study Period, and a 2-year long-term Treatment Period (Months 13 through 36). Due to the rare nature of the disease and no currently available treatment, patients [REDACTED] may continue to receive study drug until ORGN001 becomes commercially available or development has stopped. For patients receiving ORGN001 past month 36, a safety visit will occur [REDACTED]. Assessments performed during those visits are for the purposes of ongoing safety to receive ORGN001 and may only occur if ORGN001 is not yet commercially available for the patient.

The study will enroll both term and preterm neonates as well as infants and children who meet inclusion and exclusion criteria. In neonates, due to the roles that renal clearance and body weight play in the PK of ORGN001, dosing will be based upon the GA of the patient. Day 1 dosing for term (\geq 37 weeks GA) and preterm neonate (< 37 weeks GA) patients will begin with

[figure not shown]
ORGN001 IV infusions of 700 µg/kg/day and 525 µg/kg/day, respectively. ORGN001 infusions should be administered every 24 hours ± 3 hours apart while hospitalized or at home.

Based on the Investigator and SRC/DMC review of all available data prior to the first (Day 28) dose adjustment, each patient's dose may be initially escalated on or before Day 28, with incremental adjustments up to 1200 µg/kg/day by Month 3. Post administration of the increased dose, patients will undergo an electrocardiogram (ECG) as well as PK sampling. If any dose is not tolerated, the dose will be reduced based on an ad hoc consultation with the SRC/DMC (also see [Section 6.1.2](#) for rules on stopping or delaying dosing).

[REDACTED]
[REDACTED] patients
will [REDACTED] to receive daily infusions of ORGN001 [REDACTED] and will return to the clinic for study visits to assess safety, efficacy, and PK.

Every effort will be made to prevent or, if unavoidable, minimize pain that may occur in association with study-related procedures and assessments. Pain will be monitored as per protocol at each study site and treated appropriately. An alternative blood sampling schedule for infants, for whom less blood volume should be collected, must be used [REDACTED]

Figure 2: Study Design for Study ALXN1101-MCD-202^a

^a Patients who reach 36 months of treatment may continue to receive study drug until ORGN001 becomes commercially available or development has stopped. [REDACTED]

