5. SCHEDULES OF ASSESSMENTS

The detailed Schedule of Assessments for the initial 12-month Treatment Period and the Schedule for the long-term Treatment Period are provided [REDACTED] [REDACTED].

Table 10: Schedule of Assessments (Screening/Baseline and 12-Month Study Period)

Assessment	Screening / Baseline	12-Month Study Period
Study Day		
Month		
Visit Window (Days)		
Informed consent		
Eligibility		
Demographic data		
Genotype		
Family history		
Medical history		
Physical examination ^b		
Vital signs ^b		
Vital status		
Additional BP measurements ^c		
Chemistry and Hematology ^{b,d}		
Urinalysis ^{b,e}		
Growth parameters		
Feeding pattern		
Neurologic examination ^b		
Modified Glasgow Coma Scale		
Bayley-III (or WPPSI-IV) ^f		
GMFM-88 ^g		
GMFCS-E&R		
PEDI ^h		
Ophthalmologic examination		
Seizure activity ^{b,i}		

Assessment	Screening / Baseline	12-Month Study Period	
Study Day			
Month			
Visit Window (Days)			
Brain MRI ^j			
Brain ultrasound ^k (neonates only)			
ECG ^{b,l}			
EEG ^m			
PD sampling, urine			
PD sampling, blood ^{b,n}			
PK sampling ^{b,o}			
[REDACTED]			
ORGN001 infusion ^p		Daily	
Concomitant medications/procedures ^b	X	Continuous monitoring	
Assess AEs ^b		Continuous monitoring	
Follow-up Visits			

Note regarding blood samples: The total blood volume will not exceed the amount considered acceptable for the patient's clinical condition and the institution's guidelines [REDACTED]. If an Investigator decides to deviate from these limits, the deviation must be fully documented and the Investigator should provide justification for the deviation.

With agreement from the Sponsor, some Baseline assessments may be completed after dosing has begun due to urgency of study drug initiation.

^a For neonate patients born prior to 37 weeks of gestation, the Month 12 assessments will be performed at target time point, adjusted for prematurity by scheduling the visit date plus the addition of the difference between gestational age and full-term gestation of 40 weeks.

^b These assessments will be performed when any dose adjustment occurs: physical examination, vital signs, neurologic examination, ECG, PD sampling (blood), PK sampling, serum chemistry, hematology, urinalysis, evaluation for seizure activity, assessment of concomitant medications, assessment of AEs. Electrocardiograms should be performed prior to any blood draws or treatment administration scheduled for the same study visits.

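### Same-day chemistry and hematology at an unscheduled dose change differ between Section 13.3 and Table 10 footnote b, and the seven-day check depends on an SRC recommendation that such a change need not involve

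*Combined protocol and SAP*

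**What the plan says.** **Sampling on the day.** Section 13.3 (Laboratory Assessments) opens its rule with "Following recommendation by the SRC for an unscheduled dose adjustment, blood and urine samples will be collected" and names hematology, serum chemistry and urinalysis as the purpose. It then gives two steps. For the first day: "On the day of dose change, study drug will be administered at the study site. A urine sample will be collected". For the follow-up: "Seven days after the adjusted dose is administered, a blood and a urine sample will be collected at any time during this study visit".

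Table 10 footnote b, in the schedule for screening and the 12-month study period, reads: "These assessments will be performed when any dose adjustment occurs: physical examination, vital signs, neurologic examination, ECG". Its list continues with PD blood, PK, serum chemistry, hematology and urinalysis. It sets no SRC condition. Section 4.3.8 says that extra urine or blood samples may be taken when the SRC/DMC recommends an adjustment.

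**Who is consulted.** Section 6.1 lets the Investigator or Sponsor convene the SRC for an unscheduled adjustment but does not oblige them to. Section 6.1.1 states: "Dose changes will occur following consultation with the medical monitor and, if applicable, with the SRC". Section 6.1.2, Scenario 2 (a study drug-related SAE in one patient) begins: "If the treating physician, in consultation with the medical monitor, determines that a dose reduction could be expected to reduce the risk", and does not name the SRC. Section 4.1 states: "If any dose is not tolerated, the dose will be reduced based on an ad hoc consultation with the SRC/DMC".

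**What starts the schedule.** The title of Table 12, Section 13.3 and the detailed sampling lists in Sections 10 and 11 all begin from an SRC recommendation. Sections 10 and 11 also each have a general sentence covering any unscheduled dose adjustment visit. Table 16 footnote b calls for PK sampling on the first day of any dose adjustment.

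**The concern.** Sites reading different sections would handle the same event differently. One following Section 13.3 alone is not told to draw chemistry or hematology on the day of change; one following footnote b must; one following Section 4.3.8 may choose. Laboratory data around dose changes would then be uneven across patients for reasons unrelated to their condition. In a study with no control arm and no fixed sample size, each such record counts.

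The second conflict concerns which patients get the follow-up check. Unscheduled changes include those made for drug-related adverse events. If such a change is agreed between the treating physician and the medical monitor, the text that prescribes the seven-day laboratory check does not apply as worded, because its condition is an SRC recommendation.

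The panel includes creatinine and liver enzymes, and Section 4.1 gives renal clearance, with body weight, as a reason for basing the neonatal dose on gestational age. A laboratory value close to the change is thus relevant to interpreting exposure and safety.

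**Working it through.** No alpha, power, event count or sample size enters, so this is a comparison of passages.

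**Step 1: chemistry and hematology on the day of change.**

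| Place | Condition | Chemistry/hematology that day |
|---|---|---|
| Section 13.3 | SRC recommendation | Not listed (urine only); blood at seven days |
| Table 10 footnote b | Any dose adjustment, first 12 months | Required |
| Section 4.3.8 | SRC/DMC recommendation | Optional |
| Table 12 | SRC recommendation | Row present, visit cells blank in the public text |

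For an SRC-recommended change in the first 12 months, all four places apply. The two firm rules give 0 and 1 collections. No precedence between them is stated.

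**Step 2: other blood that day.** Section 10 asks for a predose PD sample on the adjustment day. Section 11 asks for PK samples at three times: end of infusion, 1 to 2 hours after it, and 3 to 4 hours after it. The conflict in Step 1 is therefore confined to chemistry and hematology.

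**Step 3: infusions before the first safety blood under Section 13.3.** Call the change day 0, with daily dosing and none missed. Days 0 to 6 give 7 infusions. If the day-7 sample follows that day's infusion, the count is 7 + 1 = 8. So the first listed chemistry and hematology result follows seven or eight infusions at the new dose, counting the one on the change day.

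**Step 4: what remains for a change made without the SRC.**

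| Check | First 12 months | After Month 12 |
|---|---|---|
| Same-day physical, neurologic, ECG, chemistry, hematology, urinalysis | Covered by footnote b | Cannot be determined: Table 11 cells blank, text before its notes redacted |
| PD and PK sampling | Covered by general sentences in Sections 10 and 11 and by footnote b | Covered by those general sentences; for PK also by Table 16 footnote b |
| Seven-day laboratory check of Section 13.3 | Not triggered as written | Not triggered as written by Section 13.3 |

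**Step 5: whether such a change is possible.** Sections 6.1 and 6.1.1 make SRC involvement conditional, and Scenario 2 in Section 6.1.2 proceeds without naming it. Section 4.1 ties reduction of a dose that is not tolerated to SRC/DMC consultation. A drug-related SAE leading to a lower dose can fall under both texts, which name different consultations.

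**The case against.** The case against has real content.

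- Section 13.3 does not forbid chemistry on the day. A site applying it together with footnote b would draw the sample in the first 12 months.
- Table 12 is the dedicated schedule and has a chemistry and hematology row; its unseen cells may already answer the first question.
- Section 6.1.2 calls its scenarios examples, Section 4.1 cross-refers to it, and the synopsis has both committees consulted ad hoc on individual cases. The texts could be read together as always involving the SRC.

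These points narrow the issue without removing it. Whatever Table 12 contains, Section 13.3 and footnote b still differ and Section 4.3.8 says something else again. If the SRC is always meant to be consulted, Section 6.1.1 should not make that conditional.

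A reader might infer more, and the documents do not support it:

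- *That no blood is taken on the day.* PD and PK blood is specified.
- *That all monitoring depends on the SRC.* Footnote b, Table 16 footnote b and the general sentences in Sections 10 and 11 do not.
- *That after Month 12 no safety checks are required.* The cells and some text are blank or redacted, and silence for that reason is not absence from the plan.
- *That a creatinine or enzyme change could not be placed before or after the new dose.* Scheduled visits or routine care may supply a recent value, and Section 6.1.1 allows laboratory data to prompt the change. It is only that Section 13.3 guarantees no value on the day.
- *That Scenario 3 shows the same gap in treated children.* Its added action limits dosing in subsequent patients, which is not clearly an unscheduled adjustment.

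**Conclusion.** The concern holds in two limited parts, and the correction should be made.

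First, for an SRC-recommended unscheduled change in the first 12 months, the current text gives incompatible instructions on same-day chemistry and hematology: none listed, required, or optional. Following Section 13.3 alone, the first such result comes after seven or eight infusions at the new dose.

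Second, the seven-day check in Section 13.3 is conditioned on an SRC recommendation, while Sections 6.1, 6.1.1 and 6.1.2 allow a change without one and Section 4.1 points the other way. For a change made without the SRC, that check is the component not triggered as written.

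The infusion count assumes daily dosing with none missed and a sample on day 7. The verdict also assumes that the blank cells of Table 12 do not state an overriding rule; even if they do, the other sections need aligning. How many patients would be affected cannot be estimated, since the documents give no rate of unscheduled changes. The overall survival analysis is unaffected.

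**What to change.** 1. Reconcile Section 13.3, Section 4.3.8, Table 10 footnote b and Table 12 so that all four state the same chemistry and hematology sampling for the day of an unscheduled dose-level change.
2. Reconcile Sections 4.1, 6.1, 6.1.1 and 6.1.2 on who is consulted before such a change.
3. Make the trigger of Table 12 and of Sections 10, 11 and 13.3 consistent with the outcome of item 2, so that it is clear whether the seven-day check applies to every unscheduled change.
4. Distinguish a change of dose level from recalculation for body weight (Sections 2.5 and 9.4), so that the trigger is not read to include routine weight updates.
5. Confirm which safety checks apply to a dose change after Month 12.

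Which sampling rule and which consultation rule prevail is for the sponsor and its clinicians.

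The cost is amendment wording. If same-day sampling is kept, some blood volume is added within the Appendix A limits (1% of total blood volume at any single time, 3% over four weeks). Appendix A gives priority to safety-relevant tests when the limit is reached, so PK or PD samples could be displaced. The size of that trade-off cannot be calculated because the sample volumes are not shown.
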